# **11. STATISTICAL CONSIDERATIONS**

## **11.1. Statistical Design**

Single arm prospective study of paired imaging studies.

## **11.2. Randomization**

This study is to compare the images from two different scans: standard SPECT/CT and digital

PET/CT and patients are scanned with both scanners. No randomization will be done.

### **11.3. Accrual estimates**

We expect accrual of 75 patients. There are approximately 100 patients receiving SIRT each year at Stanford University. We plan to enroll 25 participants/year (33%) and this is easily achievable given our experience with other protocols.

### **11.4. Criteria for future studies**

At this time, there are no future studies planned beyond the initial 75 participants.

### **11.5 Statistical Analysis**

Statistical analysis is not required for this study since the comparison is between two separate modalities with inherently different properties.

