## **5.3 Details of processing/analysis**

The  $^{99m}\text{Tc}$  MAA planar and SPECT/CT imaging and the PET/CT scans will be interpreted by ABNM certified Nuclear Medicine physicians. All investigators have significant clinical experience and will be blinded to the participant's medical history and the results of other imaging modalities. A consensus read will be obtained for each scan to assess image quality. Each lesion will be tabulated and a comparison of lesion detection and radiation absorbed dose by each scanner will be conducted.

Currently,  $^{99m}\text{Tc}$  MAA planar and SPECT/CT images only simulate  $^{90}\text{Y}$  radiopharmaceutical biodistribution within the liver and tumor(s). Incorporating SurePlan software (MIM) to analyze the PET/CT images will determine final dose-volume histogram (DVH) within the liver and tumor (s) post  $^{90}\text{Y}$  injection. Additionally,  $^{90}\text{Y}$  PET/CT and  $^{99m}\text{Tc}$  MAA planar and SPECT/CT biodistribution images can be compared to evaluate  $^{99m}\text{Tc}$  MAA simulation accuracy. Results of this image comparison could potentially impact clinical decision-making moving forward. This information will be reported and shared with the referring physicians involved in the care of the patient.

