## **10. MEASUREMENTS**

### **10.1 Primary outcome measure**

We will evaluate the image quality of the lesions detected with the digital PET/CT scanner

and compare with the image quality of the lesions seen on the standard of care pre-therapy  $^{99m}\text{Tc}$ -MAA SPECT/CT.

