## **10.2 Measurement Methods**

We will use a 5-point Likert scale to assess image quality.

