## **10.4 Response Review**

The 5-point Likert scale will be determined by Nuclear Medicine physicians blinded to the diagnosis and results of the other scan, in a randomized order to avoid bias. Two physicians will review all scans independently. Both scans of a given patient will be analyzed by one physician, then separately by the second physician.

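### Section 11.5 waives statistical analysis because the modalities differ, which leaves the paired primary comparison of image quality with no prespecified summary, no required precision and no fixed score

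*Combined protocol and SAP*

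**What the plan says.** Section 11.5 of the combined protocol and SAP is a single sentence: "Statistical analysis is not required for this study since the comparison is between two separate modalities with inherently different properties".

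The rest of the document sets up a comparison.

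- **Objective and outcome.** Section 1.1 compares the image quality of post-SIRT 90Y PET/CT with that of 99mTc-MAA SPECT/CT. Section 10.1 evaluates lesions on the digital PET/CT and will "compare with the image quality of the lesions seen on the standard of care pre-therapy" 99mTc-MAA SPECT/CT.
- **Scale.** Section 10.2: "We will use a 5-point Likert scale to assess image quality". No anchors are given; that one scale serves both modalities is an inference.
- **Design.** Section 11.1: "Single arm prospective study of paired imaging studies". Section 11.2 confirms that each patient has both scans.
- **Readers.** Section 10.4: "Two physicians will review all scans independently". The reads are blinded to diagnosis and to the other scan's results, in randomized order. Section 5.3: "A consensus read will be obtained for each scan to assess image quality".
- **Images.** Section 5.2 reconstructs the PET data in two ways and does not say which is scored.
- **Size.** Sections 3.4.1 and 11.3 give 75 patients as an accrual estimate.

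Section 1.2 adds a secondary objective worded as superior accuracy of PET/CT in distribution and dosimetry. Sections 10.5 to 10.8 address it by comparing the two modalities with each other.

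**The concern.** The reason given in section 11.5 does not lead to its conclusion. If the differences between the modalities made a comparison meaningless, the primary objective would fall with the analysis. If the comparison is worth making, it needs a summary and a statement of its uncertainty. Sections 1.1 and 11.5 therefore need to be reconciled.

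Two things are at stake. A report that followed the plan could give score summaries with no interval, so a reader could not tell how far an apparent preference might be chance. And because neither the summary nor the score is fixed, both could be chosen after the scores are known. Participants accept a research CT of up to about 5 mSv (section 8.1) to supply these data.

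**Working it through.** **1. Is the missing analysis supplied elsewhere?** Sections 10.1 to 10.4 give the scale, blinding, read order and number of readers. None gives a summary measure, an interval, a test or a rule for combining two readers. The tabulation in section 5.3 concerns lesion detection and absorbed dose; the lesion-by-lesion comparison in section 10.8 concerns dose. Neither covers the Likert score.

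**2. Is the score defined?**

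| Element | One reading | Other reading |
|---|---|---|
| Unit | Scan (5.3, 10.4) | Lesion (10.1) |
| Read | Consensus (5.3) | Two independent reads (10.4) |
| PET image | Standard iterative reconstruction (5.2) | Regularized reconstruction (5.2) |

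No passage settles any row.

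**3. The plan's own figure.** 25 participants per year × 3 years = 75, which reproduces the stated number as an accrual forecast. It cannot be checked as a power or precision calculation, because no alpha, power, effect or SD is stated.

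**4. What precision could be reported?** Half-width of the 95% interval for a mean paired difference = t(0.975, n−1) × SD / √n. The SDs are assumed. The 60-pair column supposes a 20% loss of pairs, also assumed.

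| SD of differences | n = 75 (t = 1.993) | n = 60 (t = 2.001) |
|---|---|---|
| 0.5 | 0.115 | 0.129 |
| 1.0 | 0.230 | 0.258 |
| 1.5 | 0.345 | 0.387 |

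So an interval is readily obtainable, and the differing properties of the modalities do not prevent it.

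**5. Why a bare percentage is not enough.** Suppose 45 patients score higher on PET/CT, 30 lower and none tie. The report would say that 60% favour PET/CT. The exact (Clopper-Pearson) 95% interval is 48.0% to 71.1%, and the exact two-sided sign test gives p = 0.105. Chance is not excluded.

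**6. Which summary behaves when scores tie?** Ties are likely on a 5-point scale. Suppose 35 higher, 5 lower and 35 tied.

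- Proportion higher: 35/75 = 47%, exact 95% interval 35% to 59%. This looks like no preference.
- Sign test on the 40 untied pairs: p about 0.000001.
- Proportion higher minus proportion lower: d = 35/75 − 5/75 = 0.40. SE = √[(35/75 + 5/75 − 0.40²)/75] = √(0.3733/75) = 0.0706. The approximate 95% interval is 0.40 ± 1.96 × 0.0706, or 0.26 to 0.54.

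With ties, 50% is no longer the no-difference value for the proportion higher. The difference in proportions keeps zero as its null.

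**7. If the lesion is the unit.** Design effect = 1 + (m − 1) × ICC. With an assumed 3 lesions per patient and ICC 0.5, this is 1 + 2 × 0.5 = 2.0. Ignoring it would make intervals too narrow by a factor of √2.0 ≈ 1.4.

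**8. The secondary objective.** Section 5.3 says that the "MAA planar and SPECT/CT images only simulate" the 90Y distribution, and it uses the comparison with PET/CT to judge how accurate that simulation is. PET/CT is thus the implicit yardstick. Finding it the more accurate of the two is then built in.

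**The case against.** The sponsor has a serious answer. The SPECT/CT is a pre-therapy simulation with another tracer on another scanner. The PET/CT is a post-therapy scan done the same day or the next, with contrast-enhanced CT unless contrast is omitted. A significance test would invite the reader to credit the detector with a difference that has several possible sources, and a single-arm imaging study can be purely descriptive. The limit on attribution stands in full, and no hypothesis test is essential. But the protocol does not call itself descriptive, and a descriptive study still needs a named estimate with its precision.

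Three stronger readings are tempting and should not be drawn.

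- *That section 11.5 forbids analysis, so no interval could ever be reported.* It says that analysis is not required. Paired scores will exist and an interval could be computed later. What is missing is prespecification and any requirement to report precision.
- *That the three open choices multiply to eight admissible versions of the score.* Section 5.3 ties the consensus read to the scan, so consensus by lesion does not fit its wording. Both reconstructions might be scored, and two independent reads also need a combining rule. Independent reads might precede a consensus, though nothing says so. The score is open, but the text supports no count.
- *That 75 patients is too few, or enough.* The documents give no SD and no difference that matters, so neither can be said.

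**Conclusion.** The concern holds, and it must be fixed because it affects the primary comparison. Section 11.5 states a reason that bears on interpretation and uses it to dispense with analysis. This is a stated rule that does not follow from its reason, rather than a missing detail. The consequence is a primary comparison with no prespecified summary, no required measure of precision and a score that is not fixed.

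The figures show only what could be reported: a half-width of 0.12 to 0.35 Likert points at 75 complete pairs for an SD of differences from 0.5 to 1.5. They rest on assumed SDs, one score per scan and no lost pairs, and are not evidence about this trial. The 45/30 and 35/5/35 splits are likewise invented examples.

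The superiority wording in section 1.2 is a separate and lesser point. It would remain circular even after section 11.5 is repaired.

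**What to change.** **Essential**

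1. Replace section 11.5 with one prespecified patient-level paired summary of the Likert scores and its 95% interval: either the mean within-patient difference, or the proportion higher minus the proportion lower. Do not use the proportion higher alone. Add a paired test, such as Wilcoxon signed-rank, only if a claim of difference is intended. Otherwise call the study descriptive in section 11.1 and still report the estimate and interval.
2. Define the primary score: scan or lesion (with clustering within patient handled if lesion); which read is primary and how the two readers are combined; and which reconstruction is scored. Section 10.3 aims for analysis within a month of acquisition, so scores build up during accrual. Fix the definition before further scores are read, and disclose any already read.
3. State that a score difference reflects the whole imaging procedure, not the detector alone.

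**Secondary**

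4. Reword section 1.2 as agreement or discrepancy between MAA SPECT/CT and 90Y PET/CT. Report bias and limits of agreement in Gray, allowing for several lesions per patient.

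**Cost.** Section 11.5 is rewritten, with edits to sections 1.2, 5.2, 5.3, 10.1, 10.2, 10.4, 10.8 and, if the study is to be called descriptive, 11.1. This is a protocol modification that needs IRB approval before use (section 9.1). It brings some extra analysis and a narrower secondary claim, but no extra patients, scans or readers.

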### Appendix: Inclusion/Exclusion Criteria Checklist

Inclusion Criteria (From IRB approved protocol)	Yes	No	Supporting Documentation*
1. Patient is $\geq$ 18 years old at the time of the scan			
2. Patient provides written informed consent			
3. Patient is referred for $^{90}\text{Y}$ SIRT radioembolization of liver tumor(s)			
4. Patient is capable of complying with study procedures			
5. Patient is able to remain still for duration of imaging procedure (approximately 30 minutes total for digital PET/CT)			
Exclusion Criteria (From IRB approved protocol)			
1. Patient is pregnant or nursing			

\*All subject files must include supporting documentation to confirm subject eligibility. The method of confirmation can include, but is not limited to, laboratory test results, radiology test results, subject self-support, and medical record review.

